Long-Term Follow-Up: LTFU, up to 5 years following vector administration, will be conducted to characterize the clinical outcome and the type and seriousness of adverse events following the AAV2-hCHM gene transfer, as specified in the January 2020 FDA guidance document entitled, "Long Term Follow-Up After Administration of Human Gene Therapy Products." Assessments will include adverse events, history, physical and ophthalmic examinations, blood tests, urinalysis, pregnancy outcomes (in female partners of subjects) and retinal/visual function tests. All adverse events will be collected during the LTFU period and reporting will focus on those events related to the prior administration of AAV2-hCHM and the development or

	seeks to provide longitudinal information, and should adverse				
	events occur, more timely discovery and treatment.				
Efficacy Evaluations	Efficacy will be evaluated primarily by assessing visual function, measured by standard ophthalmological tests: Ophthalmologic examination, visual acuity (VA) by ETDRS testing, visual fields (VF) by Humphrey visual field testing, including foveal and macular thresholds, Goldmann visual field test, and Octopus kinet visual field test (for subjects whose central visual field is >20° in a least 1 of the 24 meridians at the Screening/Baseline visit using Goldmann perimetry III4e isopter), as well as central field testing, reading speed, contrast sensitivity, and color vision testing. Additional efficacy endpoints will include: microperimetry, full- field light sensitivity threshold testing, and quality of life (QOL) questionnaire. Anatomical structures will be imaged by fundus photography (including low intensity autofluorescence) and by OCT.				
Pharmacokinetic Evaluations	There will be no pharmacokinetic evaluations. However, there will be assessment of post-administration vector shedding (see Safety Evaluations, below).				

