## Year 1.5

- Blood and tear collection for vector shedding, if indicated
- Ophthalmic examination
- Fundus photography (including low intensity autofluorescence)
- OCT

- QOL questionnaire
- AE and concomitant medications recording
- Partner pregnancy outcomes recording
- Retinal/visual function tests:
  - Visual acuity
  - Humphrey visual field tests
  - Octopus kinetic visual field test (for subjects whose central visual field is >20° in at least 1 of the 24 meridians at the Screening/Baseline visit using Goldmann perimetry III4e isopter)
  - Reading speed
  - o Contrast sensitivity
  - Color vision test
  - Microperimetry
  - o Full-field light sensitivity threshold testing

#### Year 2

- History and physical exam
- Urinalysis
- Blood tests, including hematology, chemistry, PBMCs for ELISpot, and reactivity to AAV2 capsid
- Blood and tear collection for vector shedding, if indicated
- Ophthalmic examination
- Fundus photography (including low intensity autofluorescence)
- OCT
- QOL questionnaire
- AE and concomitant medications recording
- Partner pregnancy outcomes recording
- Visual/retinal function tests:
  - Visual acuity
  - Humphrey visual field tests
  - Goldmann visual fields (III4e isopter)
  - Octopus kinetic visual field test (for subjects whose central visual field is >20° in at least 1 of the 24 meridians at the Screening/Baseline visit using Goldmann perimetry III4e isopter)
  - o Reading speed
  - Contrast sensitivity
  - Color vision test
  - Microperimetry
  - Full-field light sensitivity threshold testing

For evaluations after Year 2, the subject will go into the long-term follow-up phase (see section 4.5). The subject returns to the clinic for follow-up at Year 2.5 and then annual follow-up, done in the clinic, for Years 3-5 for safety evaluations, standard ophthalmologic examinations, and retinal/visual function tests. The subject is questioned about general and ophthalmic health, as

well as all adverse events including the development or exacerbation of oncologic, hematologic, neurologic, or autoimmune diseases and any female partner pregnancy outcomes.

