#### 4.5 Long-Term Follow-Up

The LTFU phase is up to 5 years following vector administration, subjects are questioned about general and ophthalmic health, all adverse events including the development or exacerbation of oncologic, hematologic, neurologic, or autoimmune diseases, as well as any female partner pregnancy outcomes. The LTFU phase is drafted based on the January 2020 FDA guidance entitled *Long Term Follow-Up After Administration of Human Gene Therapy Products*. For Years 2.5, 3, 4, and 5 visits, subjects return to the clinic for safety evaluations, standard ophthalmologic examinations, and retinal/visual function testing.

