#### LTFU Visits (Years 2.5, 3 to 5):

- An annual (Years 3 to 5) physical exam with complete history; laboratory analysis will include:
  - Hematology (CBC with differential)
  - Chemistry panel (including liver and renal function tests)
  - Urinalysis
- Ophthalmic evaluations and retinal/visual function testing:
  - Ophthalmic examination
  - OCT
  - Fundus photography (including low intensity autofluorescence)
  - Visual acuity
  - Humphrey visual field test
  - Goldmann visual fields (III4e isopter; only annually)
  - Octopus kinetic visual field test (for subjects whose central visual field is >20° in at least 1 of the 24 meridians at the Screening/Baseline visit using Goldmann perimetry III4e isopter)
  - Reading speed
  - Contrast sensitivity
  - Color vision test
  - Microperimetry
  - Full-field light sensitivity threshold testing
  - QOL questionnaire
- Adverse event reporting, including any unexpected illness and / or hospitalization. Subjects will be encouraged to monitor themselves and to assist in reporting adverse events. All adverse events should be recorded. Documentation of adverse events should include causality (unlikely, possibly, or probably related) to the vector administration procedure, investigational product, study measures and any newly arising or exacerbated clinical events in four general disease categories; oncologic, hematologic, neurologic, and autoimmune disorders.
- Investigators will maintain in the case history records of exposures to mutagenic agents and other medicinal products along with subjects' adverse event profiles. If, according to the investigator, exposure to a mutagenic agent occurred, or a medicinal product was given, prior to and thought to contribute to an adverse event, or given as a response to an adverse event, then the mutagenic agent or medicinal product will be reported to the Sponsor via case report forms.
- Concomitant medications recording
- Partner pregnancy outcomes recording

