## 8 SAFETY MANAGEMENT

#### 8.1 Clinical Adverse Events

All adverse events will be monitored throughout the active and long-term follow-up phase following vector administration. Adverse event inquiry and assessment will be conducted on an ongoing basis during study participation through the following means:

- Subject inquiry or report
- Physical observation and/or physical examination
- Laboratory and any other diagnostic test results review
- Telephone call
- E-mail
- Postal query

The toxicity reporting scale (located in the Manual of Procedures) should be used, when possible, to assess adverse events.

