#### 8.8 Reporting Timeframes

The Investigators are responsible for notifying the Sponsor or designee of all AEs, other unanticipated problems related to research, and pregnancy occurrences and outcomes in accordance with the following timeline:

Type of AE	Initial Notification (Phone, Email)	Written Report
All serious AEs, including serious SARs	24 hours	The investigator (or delegate) must submit the SAE report forms (initial and follow-up) within 24 hours to the Sponsor/designee. Local telephone and fax number for reporting from each specific participating country is provided in the Investigator Study Manual. If the minimum requirements for reporting are known, the investigator should notify Spark immediately and not wait for additional information to fully document the event. Follow-up reports will be submitted by the investigator to Spark at appropriate intervals until the SAE has resolved or, in the case of permanent impairment, until it has stabilized.
Other unanticipated problems or reportable events related to research and pregnancy occurrences and outcomes	N/A	Within 5 business days
All other AEs	N/A	Summary of AEs reported at time of continuing review As needed for sponsor reporting requirements (FDA & NIH/OBA annual reports and DSMB reports) or as specified in MOP

All AEs must be entered in the appropriate section of the CRF. To improve the quality and consistency of AE data, Investigators should observe the following general guidelines:

• Standard English medical terminology should be used rather than colloquial expressions or abbreviations.

- Whenever possible, the AE should be evaluated and reported as a diagnosis rather than as individual signs or symptoms. If a definitive diagnosis is not possible, the individual signs and symptoms should be recorded.
- If an AE requires a surgical or diagnostic procedure, the illness leading to the procedure should be recorded as the AE, not the procedure itself.

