#### 7.2 Adverse Events

All adverse events (AEs) including serious adverse events (SAEs) will be recorded through the Year 2 visit following investigational product administration. Following the scheduled Year 2 visit, adverse event recording will occur for any related serious adverse events, or for the development of any oncologic, hematologic, neurologic or autoimmune events.

An AE is any untoward, undesired, or unplanned clinical event in the form of signs, symptoms, disease, or laboratory or physiological observations occurring in a subject participating in a clinical study with the Sponsor's investigational product, regardless of causal relationship. AEs will

include any conditions that: 1) were not present prior to investigational product administration, but appeared following investigational product administration; or 2) were present prior to investigational product administration, but worsened in severity and/or frequency following investigational product administration.

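### SAP 7.2 restricts adverse event recording after Year 2, although the protocol requires all adverse events through Year 5

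*SAP*

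**What the plan says.** **SAP.** Section 7.2 opens with two sentences on recording. All AEs, serious or not, are recorded through the Year 2 visit. Then: "Following the scheduled Year 2 visit, adverse event recording will occur for any related serious adverse events", or for the development of an event in one of four classes: oncologic, hematologic, neurologic or autoimmune. Section 7.2.5 takes in every AE after administration and before end of study, serious or non-serious and regardless of relationship. Section 3.1 describes about two years of follow-up plus three years of long-term follow-up. The AE row of Appendix A is marked at Years 2.5 and 3-5.

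**Protocol (current version).**
- Synopsis, Long-Term Follow-Up: "All adverse events will be collected during the LTFU period".
- Section 4.2.2, text on evaluations after Year 2: subjects are asked about "all adverse events including the development or exacerbation of oncologic, hematologic, neurologic, or autoimmune diseases and any female partner pregnancy outcomes".
- Section 4.5: "subjects are questioned about general and ophthalmic health, all adverse events including the development or exacerbation of oncologic, hematologic, neurologic, or autoimmune diseases".
- Section 4.5, LTFU Visits: "All adverse events should be recorded". Causality documentation there extends to "newly arising or exacerbated clinical events in four general disease categories".
- Section 8.1: "All adverse events will be monitored throughout the active and long-term follow-up phase following vector administration".
- Section 8.8: "All AEs must be entered in the appropriate section of the CRF".

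**The concern.** The two documents give different rules for the same activity over the same period. In the protocol the four disease classes are examples within a complete record of AEs. In SAP 7.2 they are, with related serious events, the whole of what is recorded after Year 2.

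Safety and tolerability are the primary objective, and 7.2 opens the AE section of the analysis plan. A programmer could use it to filter post-Year-2 data, or a writer could carry it into the study report as the collection rule. The reader of that report would then take the AE profile for Years 2 to 5 as incomplete by design, or it would in fact be incomplete.

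The events at risk are not remote ones. Protocol 9.4.2 lists cataract, macular hole and reduced visual acuity among the risks of the administration procedure. None of these belongs to the four classes, so a non-serious case first noted at Year 3 would fall outside 7.2 even if judged related.

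**Working it through.** The plan states no figure to reproduce, so the check is a comparison of the texts, followed by simple arithmetic for scale.

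**1. Which events each rule covers after Year 2**

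| Event after Year 2 | Protocol 4.5 and 8.1 | SAP 7.2 | SAP 7.2.5 |
|---|---|---|---|
| Related serious AE | yes | yes | yes |
| New event in the four classes | yes | yes | yes |
| Unrelated serious AE outside the four classes | yes | no | yes |
| Non-serious AE outside the four classes, related or not | yes | no | yes |
| Worsening of a pre-existing condition in the four classes, not a related serious AE | yes | no, if read literally | yes |

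The last row turns on wording. SAP 7.2 speaks only of development, whereas protocol 4.2.2 and 4.5 name exacerbation as well.

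The 7.2.5 column assumes that end of study means the end of long-term follow-up. The SAP does not define the term, but 3.1 and Appendix A both carry the study past Year 2. The protocol column does not depend on that assumption.

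**2. Exposure time under the narrower rule**

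Inputs: 5 subjects in Dose Group 1 and 10 in Dose Group 2 (SAP 3.1); 2 years of active follow-up plus up to 3 more, 5 in total (protocol 3.1). Every subject is assumed to complete.

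Subject-years after Year 2 = subjects × 3; total subject-years = subjects × 5.

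- Dose Group 1: 5 × 3 = 15 of 5 × 5 = 25
- Dose Group 2: 10 × 3 = 30 of 10 × 5 = 50
- All subjects: 15 × 3 = 45 of 15 × 5 = 75, and 45/75 = 60%

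**3. Scheduled AE visits under the narrower rule**

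Inputs: the AE row of Appendix A. Day 0 is left out because protocol 4.2.1 lists its AE recording as pre-operative.

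- Through Year 2: Days 1, 3, 14, 30, 90, 180 and 365, Years 1.5 and 2 = 9 visits
- After Year 2: Years 2.5, 3, 4 and 5 = 4 visits
- Share after Year 2: 4/(9 + 4) = 4/13 = 30.8%, or 4/14 = 28.6% if the conditional Day 7 visit takes place

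Protocol 8.1 also provides for AE inquiry between visits, so the visit share is only a rough guide.

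**The case against.** The strongest reply is that no consequence has been shown. The protocol governs what sites collect, and it asks for everything. SAP 7.2.5 governs what is tabulated and listed, and it already specifies the right output. On that view the opening of 7.2 is stale descriptive text. This stands as far as it goes: if both are followed, the loss is zero. It does not make 7.2 correct, and the SAP does not say which of its two sections prevails.

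Four narrower points deserve an answer.

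- **Reporting emphasis.** The synopsis goes on to say that LTFU reporting will concentrate on related events and on the development of certain conditions; the sentence is cut off in the available copy. So the protocol does treat reporting differently after Year 2. But that clause concerns emphasis in reporting and follows the statement that all AEs are collected. SAP 7.2 restricts recording.
- **End of study.** Because the SAP does not define it, the conflict inside the SAP is less firm than the conflict with the protocol. It would disappear only if end of study meant Year 2, which 3.1 and Appendix A do not support.
- **Exacerbation.** The AE definition later in 7.2 includes worsening of earlier conditions, so a worsening could be read as the development of an event. The last row of the table is therefore one possible reading; the other rows do not need it.
- **Weaker supports.** Protocol 8.8 gives no time limit and does not mention LTFU, and a marked visit in Appendix A does not show that all AEs are meant. Both agree with the finding without proving it. Protocol 4.5 and 8.1 carry the weight.

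**Conclusion.** The concern holds. SAP 7.2 states a recording rule for Years 2 to 5 that contradicts protocol 4.5 and 8.1 and, on the natural reading of end of study, SAP 7.2.5. It should be fixed.

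If the rule were applied, it would cover at most 45 of 75 subject-years (60%), assuming that all 15 subjects complete five years, and 4 of 13 scheduled post-administration AE visits. No event rate is assumed, so this is not an estimate of events lost.

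The likely cause is incomplete updating. The SAP v3.0 change table for protocol v10.0 lists Appendix A, 3.1 and 4.3 but not 7.2, and 7.2.2 to 7.2.4 still cite protocol version 4.0. The documents suggest this but do not prove it.

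**What to change.** Replace the first two sentences of SAP 7.2 with:

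> All AEs and SAEs are recorded per the current protocol and Appendix A through the Year 5 (or last) visit, plus any related SAE the Investigator learns of after completion or withdrawal; TEAE summaries under 7.2.5 include all events on or after the date of administration through end of study.

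State in the same place that end of study means the Year 5 or last visit. This wording keeps AE recording at Screening/Baseline and before surgery, the post-withdrawal rule in protocol 4.4 and SAP 3.2.4, and the treatment-emergent definition in SAP 7.2.1. A separate table through Year 2 is optional.

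Housekeeping for the same revision:
- Add Years 2.5, 3, 4 and 5 to the visit list in SAP 7.4, which stops at Year 2 although SAP 4.3 and Appendix A carry eye examinations to Year 5.
- Point SAP 7.2.2 to 7.2.4 to sections 8.4 to 8.6 of the current protocol version.

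The cost is SAP wording only. The protocol already requires the data, and 7.2.5 already specifies the tables.

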### 7.2.1 Treatment-emergent Adverse Events

A treatment-emergent adverse event (TEAE) is an adverse event which occurs on or after the date of investigational product administration.

### 7.2.2 Adverse Event Severity

Please refer to Protocol Number AAV2-hCHM-101, Version 4.0, 13Nov2015, Section 8.5, page 36 for details.

#### 7.2.3 Adverse Event Relationship to Study Medication

Please refer to Protocol Number AAV2-hCHM-101, Version 4.0, 13Nov2015, Section 8.6, page 36 for details.

#### 7.2.4 Serious Adverse Events

Please refer to Protocol Number AAV2-hCHM-101, Version 4.0, 13Nov2015, Section 8.4, page 35 for details.

#### 7.2.5 Adverse Event Summaries

All AEs (serious and non-serious) occurring after investigational product administration and before the end of study, regardless of relationship to investigational product, will be included and classified by SOC and PT using MedDRA.

For treatment-emergent AEs (TEAEs), the following will be summarized and presented for the FAS subjects:

- i. the number and percentage of subjects experiencing a TEAE by SOC, PT and the greatest intensity
- ii. the number and percentage of subjects experiencing a TESAE by SOC and PT

In the summary tables, the incidence of TEAEs will be calculated by dividing the number of subjects who have experienced the event by the total number of subjects in the FAS. Thus, the incidence of TEAEs is shown in terms of the total number of subjects and not in terms of the total number of episodes. If a subject has repeated episodes of a particular TEAE, only the most severe episode, or the episode with the strongest causal relationship to investigational product, will be counted in the summary tables.

A subject with more than one type of TEAE in a particular SOC will be counted only once in the total of subjects experiencing TEAEs in that particular SOC. Since a subject could have more than one type of TEAE within a particular SOC, the sum of subjects experiencing different TEAEs within the SOC could appear larger than the total number of subjects experiencing TEAEs in that SOC. Similarly, a subject who has experienced a TEAE in more than one SOC will be counted

only once in the total number of subjects experiencing AEs in all SOCs.

All occurrences of all AEs will be listed for each subject, grouped by dose cohort. The listing will contain the following information: dose cohort, verbatim term, SOC, PT, severity, relationship to study medication/surgical procedure/study measure, date and day of onset, date and day of resolution, treatment given to treat the adverse event, the outcome, whether the event was an SAE, whether it led to withdrawal and whether it is a TEAE. Listings will be sorted by subject identification number, onset date, SOC, and PT. If the onset date is completely missing, then these events will be presented first. If the onset date is missing a month or a day, then these events will be presented before any complete dates.

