#### 3.2 Allocation to Study Groups

This is an open label, non-randomized, inter-subject dose escalation safety study (Phase 1/2) of the unilateral administration of two vector doses (up to  $5 \times 10^{10}$  vg per eye and up to  $1 \times 10^{11}$  vg per eye) in subjects with choroideremia, with at least 2 weeks between vector administrations to successive subjects for the first two subjects of a given dose group (study-wide) and at least 2 weeks between vector administrations per clinical site for the rest of the subjects in the given dose group. The Dose Group 1 will be administered vector first, followed by the Dose Group 2. Dose escalation will be contingent upon DSMB approval following review of safety data of the prior cohort through at least a minimum of 30 days (that is, at least a minimum of 30 days after the last subject of the prior cohort is injected). More than fifteen subjects may enroll (signing of the gene therapy study informed consent), to produce fifteen evaluable and injected subjects. Those subjects who are enrolled and fail to meet eligibility, or who are withdrawn prior to vector injection, can be replaced so that up to fifteen evaluable subjects are administered the investigational product.

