## 3. INVESTIGATIONAL PLAN

### 3.1 Study Design

This is an open label, non-randomized, inter-subject dose escalation safety study (Phase 1/2) of two vector doses (up to  $5x10^{10}$  vg per eye (Dose Group 1) and up to  $1x10^{11}$  vg per eye (Dose Group 2)) administered unilaterally, with at least 2 weeks between vector administrations to successive subjects for the first two subjects of a given dose group (study-wide) and at least 2 weeks between vector administrations per clinical site for the rest of the subjects in the given dose group. The eye with worse visual acuity will be injected, unless the subject prefers that eye, in which case the contralateral (non-preferred) eye will be injected.

Five subjects will be entered to Dose Group 1 and ten to Dose Group 2. All subjects must meet entry criteria detailed in the Protocol Section 3.4. Dose escalation will be contingent upon DSMB review of the safety data through at least 30 days for all subjects in the prior cohort. Subjects will be followed up for safety and efficacy evaluations for approximately 2 years post vector administration, then additional 3 years of long-term follow-up. See Appendix A for the Schedule of Assessments.

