## 4. GENERAL CONSIDERATIONS FOR DATA ANALYSIS

Due to the small sample size there are no statistical hypotheses regarding treatment effects. Rather, displays and comparisons of study results – regarding dose-related safety and efficacy among the dose cohorts – will primarily utilize descriptive statistics, as noted below.

Unless otherwise specified, continuous variables will be summarized by presenting the number of non-missing observations (n), mean, standard deviation, median, minimum, and maximum. Categorical variables will be summarized by presenting the number and percentage of subjects for each category.

Summary results will be provided for each dose cohort. All tabulations will be based on pooled data across study sites.

Analyses will be performed using SAS for Windows statistical software, version 9.2 or higher (SAS, Cary, NC), except where other software may be deemed more appropriate.

CTI will perform all efficacy and safety statistical analyses.

Subject data will be listed, sorted by dose cohort and subject number.

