# 4.2 Analysis Sets

The full analysis set (FAS) is defined as all subjects who have received the investigational product. All efficacy and safety analyses will be performed on the FAS.

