### 8. **DSMB COHORT REVIEW**

In this trial, dose escalation will be contingent upon DSMB approval following review of the safety and efficacy data through at least 30 days for all subjects in the prior cohort. The data for DSMB analysis will be presented as described above. Following each DSMB meeting, the DSMB will

provide the Sponsor with written recommendations related to continuing, changing, or terminating the trial.

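### Adverse event percentages shown to the DSMB during or soon after Dose Group 2 enrolment ignore unequal follow-up and can understate later-onset events in the higher-dose cohort

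*SAP*

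**What the plan says.** SAP 7.2.5 gives one incidence measure for treatment-emergent events, obtained by "dividing the number of subjects who have experienced the event by the total number of subjects in the FAS". SAP 4.2 sets no minimum follow-up for that denominator: "The full analysis set (FAS) is defined as all subjects who have received the investigational product". SAP 4 states "Summary results will be provided for each dose cohort", and describes the displays as comparisons "regarding dose-related safety and efficacy among the dose cohorts". Cohort sizes are in SAP 3.1: "Five subjects will be entered to Dose Group 1 and ten to Dose Group 2".

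SAP 8 applies the same displays to the DSMB: "The data for DSMB analysis will be presented as described above". The one DSMB review whose content it specifies is the escalation review, a "review of the safety and efficacy data through at least 30 days for all subjects in the prior cohort".

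Protocol 3.2 makes dosing sequential: "The Dose Group 1 will be administered vector first, followed by the Dose Group 2". Escalation waits at least 30 days after the last Dose Group 1 injection, and injections are at least two weeks apart (study-wide for the first two subjects of a group, then per site). Protocol 9.4.1 has the DSMB meet at least once a year during enrolment. SAP 7.1 (Extent of Exposure) covers dose, volume and retinotomy sites, but not duration of follow-up.

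**The concern.** A crude percentage over everyone injected treats a subject injected last week as fully observed for events that take months to appear. When one cohort is injected after the other and the table is cut while the second is still young, the two percentages cover different lengths of observation. The error runs one way: the later cohort, here the higher dose, looks safer than it is.

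Safety is the primary objective, and the SAP says these displays serve to compare dose-related safety. Late events matter for this product. Protocol 9.4.2 reports focal photoreceptor loss in monkeys at 3 months, at the higher of the two doses tested, that was absent at 3 weeks. An event with that timing could not yet have appeared in recently injected Dose Group 2 subjects, who would still count as event-free.

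**Working it through.** The documents state no adverse event rate, enrolment dates or look dates, so there is no plan figure to reproduce. The hazards, injection schedules and cut dates below are assumptions. Both cohorts have the same true risk throughout, so a ratio of 1.00 means no distortion.

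**Formula.** Expected crude incidence in a cohort = mean over its injected subjects of 1 − exp(−H(t)), where t is time from injection to the data cut and H is the cumulative hazard. Each cohort's own number is the denominator.

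**1. Constant hazard, month 12.** The Protocol synopsis gives about 3.5 years including a 2-year active phase, so about 1.5 years of enrolment. Assume Dose Group 1 is injected at months 0, 0.5, 1, 1.5 and 2, Dose Group 2 evenly over months 3 to 18, and a hazard of 0.5 per year.

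- Dose Group 1 (follow-up 12 to 10 months): 0.393, 0.381, 0.368, 0.354, 0.341; mean 36.7%.
- Dose Group 2, six of ten injected (follow-up 9, 7.33, 5.67, 4, 2.33, 0.67 months): 0.313, 0.263, 0.210, 0.154, 0.093, 0.027; mean 17.7%.
- Ratio 17.7/36.7 = 0.48. Hazards of 0.25 to 1.0 per year give 0.46 to 0.52.
- At hazard 0.5, the month-18 ratio is 25.4/50.7 = 0.50 (counting the subject injected that day) and the month-24 ratio is 41.9/61.6 = 0.68.

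**2. Mainly early onset.** Protocol 7.3 says that events after two weeks are generally complications of earlier ones. Put 80% to 95% of the hazard in days 0 to 14, spread the rest evenly to day 730, and let 2-year risk be 20%, 50% or 80%. Use three schedules:

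- (a) fastest pace, one site: Dose Group 1 days 0–56, Dose Group 2 days 86–212;
- (b) fastest pace, two sites in Dose Group 2: days 86–156;
- (c) even accrual over 1.5 years: days 0–159, then 189–547.

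| Look | Constant hazard | 80–95% in days 0–14 |
|---|---|---|
| Day of last Dose Group 2 injection | 0.23–0.48 | 0.78–0.90 |
| 30 days later | 0.38–0.53 | 0.92–1.00 |

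With 50% of the hazard in days 0 to 14, the ratio 30 days after the last injection is 0.78 to 0.93. On the month-12 schedule of step 1, 80% to 95% early onset gives 0.95 to 0.99.

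**3. Events possible only after day 91.** Schedule (a), hazard 0.5 per year after day 91, cut 30 days after the last injection (day 242).

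- Dose Group 1, days at risk 151, 137, 123, 109, 95: mean of 1 − exp(−0.5 × days/365.25) = 15.5%.
- Dose Group 2, days at risk 65, 51, 37, 23, 9 and five zeros: 0.245/10 = 2.5%.
- Ratio 0.16. Hazards of 0.25 to 1.0 give 0.15 to 0.17, with five of ten Dose Group 2 subjects past day 91.
- Schedule (c) at the corresponding cut gives 0.33 to 0.40. Schedule (a) at day 365 gives 0.53 to 0.58.

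**4. Where it cannot arise.** The escalation review contains no Dose Group 2 subjects. Once every subject has completed the same follow-up, the ratio is 1.00 in every scenario, withdrawals aside.

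**5. Denominator wording.** Read literally, the whole analysis set is 15 for both cohorts. At an equal 40% risk that gives 2/15 = 13% against 4/15 = 27%, a distortion in the opposite direction. SAP 4 makes 5 and 10 the sensible reading, but SAP 7.2.5 does not say so.

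**The case against.** The strongest reply is that little turns on this percentage. The toxicity and halting rules in Protocol 7.4 are triggered by individual subjects, so late-injected subjects do not dilute them. No formal cohort comparison is planned (SAP 7), the trial is open label, and the DSMB reviews all adverse events (Protocol 8.8) and sets its own monitoring guidelines (Protocol 9.4.1). Listings give onset day for each event, and the visit-by-visit listings let a reader work out how far each subject has got. In the month-12 example the expected counts are about 1.8 of 5 against 1.1 of 6, a gap of less than one subject. The monkey finding was histopathology, and the nearest clinical measures (OCT, microperimetry, fundus photography) are listed by eye and visit without this denominator.

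All of that stands and limits the consequence. It does not repair the table. The adverse event listing shows onset only for subjects with events, so the observation time of event-free subjects must be pieced together from other listings. The expectation of early onset in Protocol 7.3 rests on the RPE65 trials, which used a different transgene.

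A reader might infer that the DSMB will see Dose Group 2 as half as toxic. The documents do not support that as a general statement: it needs a roughly constant hazard and a look during or soon after Dose Group 2 enrolment, and neither is stated. Nor do they support a claim that the escalation decision or the final table is biased.

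**Conclusion.** The point holds in a limited form. At DSMB looks during or soon after Dose Group 2 enrolment, the stated incidence rule takes no account of unequal follow-up and can understate later-onset events in the higher-dose cohort. The size is governed by onset timing and look date. It is negligible to small for events confined mainly to the first two weeks once a month has passed since the last injection, about a halving under a constant hazard at month 12, and much larger for events starting only after about three months. These figures rest on the assumed schedules and hazards, so they show a range and do not predict a result. The problem is one of interim display. It merits correction because the change is cheap and safety is the primary objective.

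**What to change.** Amend SAP 7.2.5 and SAP 8 so that the DSMB tables:

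- show median and range of follow-up for each cohort beside the crude percentages;
- state that each cohort's own number of injected subjects is the denominator;
- add incidence of treatment-emergent events and serious events by cohort in fixed post-injection windows, for example through Day 30, Day 90 and Day 365. Restrict numerator and denominator to subjects who have reached the end of the window or were followed until withdrawal, or else give a Kaplan-Meier estimate of time to first event.

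A denominator of subjects under observation at the start of a window is not enough, because it still counts those who have not completed the window.

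A single overall person-time rate should not replace these displays. With 95% of the hazard in the first two weeks, schedule (a), 30 days after the last injection, has a crude ratio of 0.99 and a mean follow-up ratio of 93/214 = 0.43. The rate ratio would then be about 0.99/0.43 = 2.3 against Dose Group 2 at identical risk. A common fixed window gives an expected ratio of 1.00 whatever the onset pattern, withdrawals aside.

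The cost is a few lines of SAP text and one extra table program using injection, onset and last-visit dates. Cells will be sparse with 5 and 10 subjects, so the window table is best kept to overall and serious events, with selected terms where needed.
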